9.4. Sample Handling

No samples will be taken.

9.5. Early Discontinuation/Withdrawal of Participants

During the course of the trial a participant may choose to withdraw early from the trial treatment at any time. This may happen for a number of reasons, including but not limited to:

- The occurrence of what the participant perceives as an intolerable AE.
- Inability to comply with trial procedures
- Participant decision

Participants may choose to stop study assessments but may remain on study follow-up.

Participants may also withdraw their consent, meaning that they wish to withdraw from the study completely. Patients are allowed to withdraw at any time. In case of withdrawal, they will communicate it to the staff who will log the withdrawal on the spreadsheet together with the reason. The patients will remain under regular active follow up

- 1) Participants can withdraw from the study but permit data obtained up until the point of withdrawal to be retained for use in the study analysis. No further data would be collected after withdrawal.
- 2) Participants can withdraw completely from the study and withdraw the data collected up until the point of withdrawal. The data already collected would not be used in the final study analysis.

In addition, the Investigator may discontinue a participant from the trial treatment at any time if the Investigator considers it necessary for any reason including, but not limited to:

- Pregnancy

The type of withdrawal and reason for withdrawal will be recorded in the CRF.

If the participant is withdrawn due to an adverse event, the Investigator will arrange for follow-up visits or telephone calls until the adverse event has resolved or stabilised.

9.6. Definition of End of Trial

The study ends 12 months after the first patient has been recruited or when restrictions to clinical practice due to the pandemic are lifted.

10. TRIAL INTERVENTIONS

Not applicable

11. SAFETY REPORTING

The study is low risk however, in the event of an adverse event (AE) or serious adverse event (SAE) occurring to a participant this would be reported as per the below.

11.1. Adverse Event Definitions

Adverse Event (AE)	Any untoward medical occurrence in a participant to whom a medicinal product has been administered, including occurrences which are not necessarily caused by or related to that product.
Device deficiency	Inadequacy of a medical device with respect to its identity, quality, durability, reliability, safety or performance. Device deficiencies include malfunctions, use errors and inadequate labelling. Device deficiencies that did not lead to an adverse event, but could have led to a medical occurrence if suitable action had not been taken, or intervention had not been made or if circumstances had been less fortunate
User error	Act or omission of an act that results in a different medical device response than intended by the manufacturer or expected by the user. Use error includes slips, lapses and mistakes. An unexpected physiological response of the subject does not itself constitute a use error.

NB: to avoid confusion or misunderstanding of the difference between the terms “serious” and “severe”, the following note of clarification is provided: “Severe” is often used to describe intensity of a specific event, which may be of relatively minor medical significance. “Seriousness” is the regulatory definition supplied above.

The following definitions will be used to determine the severity rating for all adverse events:

- Mild: awareness of signs or symptoms that does not interfere with the subject's usual activity or is transient that resolved without treatment and with no sequelae.
- Moderate: a sign or symptom, which interferes with the subject's usual activity.
- Severe: incapacity with inability to do work or perform usual activities.

11.2. Assessment results outside of normal parameters as AEs and SAEs

All adverse events (including ADEs) and device deficiencies occurring during the course of the study will be recorded on the CRF whether or not attributed to the trial device. The information recorded will include but not be limited to:

- A description of the event
- The dates of the onset and resolution
- Action taken
- Outcome
- Assessment of relatedness to the device
- Whether the AE is serious or not
- Whether the AE arises from device deficiency
- Whether the AE arises from user error

The severity of events will be assessed on the following scale: 1 = mild, 2 = moderate, 3 = severe.

Issues with the device will also be logged on the study spreadsheet using the APP-ISSUE code.

AEs/ADEs considered related to the device as judged by a medically qualified investigator or the Sponsor will be followed either until resolution, or the event is considered stable.

It will be left to the Investigator's clinical judgment to decide whether or not an AE/ADE is of sufficient severity to require the participant's removal from the study. A participant may also voluntarily withdraw from the study due to what he or she perceives as an intolerable AE/ADE. If either of these occurs, the participant must undergo an end of trial assessment and be given appropriate care under medical supervision until symptoms cease, or the condition becomes stable.

11.3. Assessment of Causality

The relationship of each adverse event to the trial must be determined by a medically qualified individual according to the following definitions:

Related: The adverse event follows a reasonable temporal sequence from trial. It cannot reasonably be attributed to any other cause.

Not Related: The adverse event is probably produced by the participant's clinical state or by other modes of therapy administered to the participant.

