11.6. Reporting Procedures for Serious Adverse Events

A serious adverse event (SAE) occurring to a participant should be reported to the REC that gave a favourable opinion of the study where in the opinion of the Chief Investigator the event was 'related' (resulted from administration of any of the research procedures) and 'unexpected' in relation to those procedures. Reports of related and unexpected SAEs should be submitted within 15 working days of the Chief Investigator becoming aware of the event, using the HRA report of serious adverse event form (see HRA website).

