17. ETHICAL AND REGULATORY CONSIDERATIONS

17.1. 6MWT

6MWT testing is very safe and is used in many conditions including in people with heart failure. However, as can occur with all forms of exercise, very occasionally some people have significant changes in their heart rate and rhythm that require medical attention. The participants undergoing the app-based 6MWT will be provided with a checklist for them to assess themselves with, and would not undertake a test if they fail this.

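### The causality categories in section 11.3 are strict and leave a gap between them, and they do not match the tests of relatedness in 11.2, 11.4 and 11.6

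*Combined protocol and SAP*

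**What the plan says.** Section 11.3 of the combined protocol and SAP makes the assessment compulsory: "The relationship of each adverse event to the trial must be determined by a medically qualified individual", using two definitions. The first has two conditions, one of timing and one of exclusion: "Related: The adverse event follows a reasonable temporal sequence from trial. It cannot reasonably be attributed to any other cause". Not Related is a positive test of its own: "The adverse event is probably produced by the participant's clinical state or by other modes of therapy administered to the participant". There is no third category.

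Other parts of section 11 ask about something else. The CRF list in 11.2 includes "Assessment of relatedness to the device", and 11.4 repeats the device as the object of the CRF entry, but then ties follow-up of non-serious events to relatedness to the trial. Section 11.6 asks for the Chief Investigator's opinion on whether a serious event arose from carrying out a research procedure, and whether it was unexpected. If both hold, a deadline applies: "Reports of related and unexpected SAEs should be submitted within 15 working days of the Chief Investigator becoming aware of the event".

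Section 17.1 names the risk of the walk itself: "very occasionally some people have significant changes in their heart rate and rhythm that require medical attention".

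**The concern.** The participants are outpatients of cardiovascular clinics (8.1), so the underlying disease will often be a reasonable explanation for a cardiac event during exercise. A definition of Related that fails as soon as one other cause is reasonable is therefore hardest to meet for the kind of event that 17.1 warns about, even when the walk plausibly contributed.

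Two actions depend on the label: the report to the REC (11.6) and the follow-up of related events (device-related in 11.2, trial-related non-serious in 11.4). Little stands behind the label to correct it. Section 14.1 states that no risk assessment was done, 14.2 plans no monitoring, and 14.4 provides no safety committee, although section 14 leaves audit possible. The study also asks for exertion beyond usual care: in Part 2, 15 patients are invited to do 10 extra walks each (15 × 10 = 150 if all are completed), of which 5 each (15 × 5 = 75) are on paths chosen to be difficult for the app.

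**Working it through.** No arithmetic applies. The check is to set out the logic of 11.3, compare the sections, and follow one event through them.

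**Logic of 11.3.** Let A be a reasonable temporal sequence, B be that some other cause is reasonable, and C be that the clinical state or another therapy is the probable cause.

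- Related = A and not B.
- Not Related = C.
- A probable cause is also a reasonable one, so C implies B. The two categories never overlap.
- They do not cover everything. Left over is every event with not C and (B or not A).

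**An event during or soon after a walk (A holds).**

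| Standing of the disease as a cause | Category under 11.3 |
|---|---|
| Not reasonable, and no other cause is reasonable | Related |
| Reasonable but not probable | Neither |
| Probable, even if the walk contributed | Not Related |

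Only the first row gives Related. In the second and third rows, a contribution from the walk does not change the result.

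**The sections compared.**

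| Section | Related to what | Test | What depends on it |
|---|---|---|---|
| 11.2 | Device | None stated | CRF entry; follow-up of device-related events |
| 11.3 | Trial | Timing, and no other reasonable cause | The formal causality label |
| 11.4 | Device (CRF entry), trial (follow-up) | None stated | Follow-up of non-serious related events |
| 11.6 | Research procedures | Event arose from the procedure, in the Chief Investigator's opinion | REC report, if also unexpected |

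No section says that the 11.3 definitions apply in 11.6, or that they do not.

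**One event traced.** Take a serious rhythm disturbance during an app-based walk, with the disease a reasonable but not probable cause.

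1. Under 11.3 it is not Related, because another cause is reasonable. It is not Not Related either, because that cause is not probable.
2. On the CRF it may be unrelated to the device, since the app worked as intended.
3. Under 11.6 the answer depends on which definition governs. If 11.3 governs, the event is not related and no report is due. If the wording of 11.6 stands alone, the Chief Investigator can call it related.
4. Even then, it must also be unexpected, and 17.1 already describes rhythm changes.
5. On every branch it is recorded on the CRF, because 11.2 records all adverse events whatever their attribution.

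**The case against.** The strongest reply is that the wording leaves room for judgement and that other provisions catch these events. Much of this stands.

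- A reader might infer that exertional events default to Not Related. The text has no default: that category needs a probable cause in the clinical state or other therapy. Some events fall there and others fall nowhere.
- A reader might infer that such events can never be Related, or that the count is driven to zero. The documents do not support that. A medically qualified person judges each case, a chronic diagnosis is not automatically a reasonable cause of a particular event, and 8.3 excludes people who cannot complete the walk or whose other illness would put them at risk. A fall on the route, for example, need not be put down to heart disease.
- A reader might infer that these events escape the REC report. That is not established, because 11.6 has its own test and does not require other causes to be excluded.
- A reader might infer that only related events are followed up. Sections 9.5 and 11.2 provide for follow-up or care of participants who leave because of an adverse event, with no condition on cause.
- The condition that the event be unexpected is a separate filter, and a better causality definition does not remove it.
- The study is described as low risk, some patients use the app regardless of it, a self-check precedes the walk, and no listed outcome uses the causality label.

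These points limit the consequences. They do not close the gap between the two categories or settle which of the differing tests applies.

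**Conclusion.** The point holds as a defect in a stated rule. The definitions in 11.3 can exclude from Related an exertional event to which the walk may have contributed, and they leave some events with no category. They also disagree with 11.6 on the test and with the CRF items in 11.2 and 11.4 on the object. As a result, an event may miss the REC report or the follow-up of related non-serious events, or two assessors may label it differently with equal support from the text.

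The size cannot be given as a number, because the documents state no event rates. The conclusion rests on the wording and on one assumption: that underlying disease will often be a reasonable alternative cause in this population. The gap in 11.3 and the mismatch between sections do not need that assumption. No estimate of app use, accuracy or usability is affected. The matter should be corrected, in proportion to a low-risk study.

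**What to change.** Use one exhaustive definition in 11.2, 11.3, 11.4 and 11.6:

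- **Related:** there is a reasonable possibility that a study procedure (including the app-based walk) or the app caused or contributed to the event, even if another cause is also possible.
- **Not Related:** there is no such reasonable possibility.

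The second is the negation of the first, so every event can be classified. Naming the walk matters because 9.1 (Recruitment) says that some patients already use the app outside the study, which leaves open whether their walks count as research procedures. The CRF item should ask about the same object as 11.3, with device deficiency kept as its separate entry, and 11.6 should refer to the definition in 11.3.

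The cost is a few sentences in section 11, a matching CRF item, and probably a few more events classed as related. The condition in 11.6 that the event be unexpected is unchanged, so the fix does not guarantee that the events named in 17.1 reach the REC.

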11.4. Procedures for Reporting Adverse Events

All AEs occurring during the safety window for the trial as defined above that are observed by the Investigator or reported by the participant, will be reported on the trial CRF,

The following information will be reported on the CRF: description, date of onset and end date, severity, assessment of relatedness to trial device and action taken. Follow-up information should be provided as necessary.

The severity of events will be assessed on the following scale: 1 = mild, 2 = moderate, 3 = severe.

Non-serious AEs considered related to the trial as judged by a medically qualified investigator or the Sponsor will be followed up until the event is stable.

11.5. Definition of Serious Adverse Events

A serious adverse event is any untoward medical occurrence that:

- results in death
- is life-threatening
- requires inpatient hospitalisation or prolongation of existing hospitalisation
- results in persistent or significant disability/incapacity
- consists of a congenital anomaly or birth defect.

Other 'important medical events' may also be considered a serious adverse event when, based upon appropriate medical judgement, the event may jeopardise the participant and may require medical or surgical intervention to prevent one of the outcomes listed above.

NOTE: The term "life-threatening" in the definition of "serious" refers to an event in which the participant was at risk of death at the time of the event; it does not refer to an event which hypothetically might have caused death if it were more severe.

11.6. Reporting Procedures for Serious Adverse Events

A serious adverse event (SAE) occurring to a participant should be reported to the REC that gave a favourable opinion of the study where in the opinion of the Chief Investigator the event was 'related' (resulted from administration of any of the research procedures) and 'unexpected' in relation to those procedures. Reports of related and unexpected SAEs should be submitted within 15 working days of the Chief Investigator becoming aware of the event, using the HRA report of serious adverse event form (see HRA website).

12. STATISTICS

12.1. Description of Statistical Methods

The analysis of the data involves reviewing the spreadsheet. The use of the labels will simplify analysis and will avoid manual coding. The R programming environment will be used to compute statistics.

To assess whether patients are able and willing to use a smartphone app for the 6MWT.

For each recruited patient, we will compute the number of app-based 6MWT results available since they confirmed that they have downloaded the app. From this number, we will compute a histogram of the number of available app-based 6MWT per patient and the percentage of participants who perform at least one app-based 6MWT prior to every consultation.

To assess the accuracy of the app-based measurement.

We will compare the walked distance measured by the app with the distance measured by the trundle wheel for those tests that provide both information. We will compute descriptive statistics (mean, standard deviation, percentiles) of the difference and BlandAltman plots.

To assess whether differences in distance walked according to the app altered management of patients.

We will use the codes related to clinical evaluations to compute descriptive statistics about the frequency of those evaluations and about how many of them were triggered by observed changes of the 6MWD.

To assess the usability and acceptance of the app.

We will compute descriptive statistics of the results of the usability and acceptance questionnaires. We will use thematic content analysis to analyse the interview transcripts.

To collect raw data from phones' sensors to allow the development of future algorithms for app-guided 6MWT.

We will also use the sensors data sent from patients involved in part 2 of the study to identify strategies to improve the algorithm that computes the distance. The availability of this type of data would be unique and would open interesting research in computer science and biomedical engineering. The University of Malmo is planning to experiment signal processing (Kalman filters, FIR filters) and machine learning (LSTM RNN) techniques to improve the accuracy of the current GPS-based algorithm and to explore the possibility to develop an indoor version of the algorithm based purely on the inertial sensors (acceleration).

To determine whether the use of the 6MWT reduces time spent and number in hospital visits.

We will estimate the time spent in hospital attendances and the number of hospital visits made during the study period and compare it with previous 5 years.

Compare the use of 6MWT during pandemic with standard care.

We will compute statistics regarding the number of 6MWT available per patient over the last 5 years and compare them with the number of available 6MWT results within the study period. This will help identify the difference between the number of 6MWT per patient per year before the pandemic (standard 6MWT in clinic) and after the pandemic (using the app).

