3. SYNOPSIS

The Trial will review the use of a mobile-based 6MWT by hospital outpatients during the coronavirus pandemic and evaluate its use

Trial Title	Evaluation of the usefulness of adopting remote, mobile-based 6MWT among hospital outpatients (the 6-APP now Study), within the constraints imposed by the SARS-COV2 pandemic.		
Internal ref. no. (or short title)	6-APPnow Study		
Trial registration	Clinical Trials. gov		
Sponsor	Oxford University Hospitals NHS Foundation Trust [name]		
Funder	NIHR BRC and the Swedish Knowledge Foundation		
Trial Design	Patient survey to evaluate their use of the 6 minute walk test smartphone app as a surrogate for regular clinic 6MWT.		
Trial Participants	Patients using 6 minute walk tests for managing cardiopulmonary function or disease management		
Sample Size	250-500 patients attending the outpatient clinics		
Planned Trial Period	Q2 2021 – Q2 2022		
Planned Recruitment period	Q2 2021 – Q2 2022		
	Objectives	Outcome Measures	Timepoint(s)
Primary	To assess whether patients are able and willing to use a smartphone app for the 6MWT	Percentage of participants who perform at least one app-based 6MWT before patient consultation.	At 3, 6, 9 and 12 months after the start of the study.
Secondary	
To assess the accuracy of the app-based measurement.
 
To assess whether differences in distance walked altered management of patients.
	
Measurement of walked distance (6MWD) measured by the app compared with a trundle wheel reference.
 
Number of clinical investigations and multidisciplinary team discussion triggered by variations in app-based 6MWD.
	
12 months
 
At 3, 6, 9 and 12 months after the start of the study.

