6. OBJECTIVES AND OUTCOME MEASURES

The population to be studied is composed of hospital outpatients who have conditions where the 6MWT is routinely used in clinical care, and/or are using the 6APP as an alternative.

The objective is: To evaluate the usefulness of adopting remote, mobile-based 6MWT among hospital outpatients, within the constraints imposed by the SARS-COV2 pandemic.

Objectives	Outcome Measures	Timepoint(s) of evaluation of this outcome measure (if applicable)
Primary Objective To assess whether patients are able and willing to use a smartphone app for the 6MWT	Percentage of participants who perform at least one app-based 6MWT before patient consultation.	At 3, 6, 9 and 12 months after the start of the study.
Secondary Objectives To assess the accuracy of the app-based measurement. To assess whether differences in distance walked according to the app altered management of patients.	Comparison of walked distance (6MWD) measured by the app versus a trundle wheel reference. Number of clinical investigations and multidisciplinary team discussion triggered by variations in app-based 6MWD.	12 months. At 3, 6, 9 and 12 months after the start of the study.

To assess the usability and acceptance of the app.	Standard usability and acceptance questionnaires, semi-structured interviews.	12 months.
To collect raw data from phones' sensors to allow the development of future algorithms for app-guided 6MWT.	Localisation position (GPS), speed, acceleration, step count, gyroscope samples collected during 6MWT.	12 months.
To determine whether the use of the 6MWT reduces time spent and number in hospital visits.	Time spent in hospital attendances and number of hospital visits made during use of the 6MWT compared with previous periods.	12 months.
To compare the use of 6MWT during pandemic with pre-pandemic use.	Total number of 6MWTS performed during 2020 pandemic period compared with pre-pandemic period.	12 months.

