9. TRIAL PROCEDURES

9.1. Recruitment

Outpatients undergoing follow up in the cardiovascular outpatient clinics in Oxford will be eligible for participation. Some of these patients are already using the app, regardless of the study, for example in the case of the pulmonary hypertension clinic. They will be approached by a member of the clinical team for consideration and recruited during a regular consultation either via phone call or during a visit in the clinic. They will be asked to download the app over the Internet.

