9.2. Screening and Eligibility Assessment

Patients will be screened every week according to the scheduled clinic phone calls or visits. A list of candidates who match inclusion and exclusion criteria (except use of smartphone) will be prepared before consultation.

During the consultation, patients will be asked about their access and fluency with smartphones to further verify compliance with the criteria.

The subgroup of 15 patients will be chosen among those using the app depending on the frequency of their use of the app and general willingness to participate in the study.

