12.3. Analysis Populations

All participants.

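### The primary outcome has two definitions: Section 12.1 requires an app test before every consultation, the synopsis and Section 6 do not say so, and the per-patient total in Section 12.1 cannot yield the stricter version

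*Combined protocol and SAP*

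**What the plan says.** The synopsis gives the primary outcome as "Percentage of participants who perform at least one app-based 6MWT before patient consultation", and the Section 6 table repeats it. Both set the evaluation times as "At 3, 6, 9 and 12 months after the start of the study". The word consultation has no article or quantifier in either place.

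Section 12.1 is the only place that says how the outcome is calculated. It starts from one count per patient: "For each recruited patient, we will compute the number of app-based 6MWT results available since they confirmed that they have downloaded the app". It continues: "From this number, we will compute a histogram of the number of available app-based 6MWT per patient", and from the same count it takes the "percentage of participants who perform at least one app-based 6MWT prior to every consultation".

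Section 12.3 gives the analysis population as "All participants". Under Section 9.1 (Recruitment), patients are "recruited during a regular consultation either via phone call or during a visit in the clinic". Section 9.3 (Subsequent Visits) has the clinician log coded, dated events at each contact. One code records a shared app test. No code records a consultation at which no test was shared.

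**The concern.** A patient who does one app test and then skips it at three later consultations is a success if one test is enough, and a failure if a test is needed before every consultation. The plan supports both answers. The study is descriptive, so this percentage is itself the primary result, and two analysts following different sections would report different figures from the same spreadsheet.

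The second problem is internal to Section 12.1. The quantity it names cannot be obtained from the quantity it says to use. An analyst following the text literally must either report something other than what is stated or devise an unplanned rule, possibly after seeing the data.

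**Working it through.** The plan states no expected percentage, threshold or calculated sample size for this outcome, so there is no figure of its own to reproduce.

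**Step 1. Do the definitions coincide?** Only if each participant has a single consultation. The document points the other way. Section 5.3 describes regular telephone contact, Section 5.4 says app results are used to follow trends, and Section 9.3 logs events at each consultation. The number of consultations per patient is not given.

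**Step 2. What can the total deliver?** Let a patient have k consultations, with x₁, …, x_k tests before each, and total T = x₁ + … + x_k.

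- *At least one* means T ≥ 1, so the total settles it. The zero bin of the planned histogram is the complement.
- *Every* means each xᵢ ≥ 1. With k = 4, both 1,1,1,1 and 4,0,0,0 give T = 4; the first meets it and the second does not. With k = 3, the same holds for 1,1,1 and 3,0,0 (T = 3).
- In general, for k ≥ 2 and no cap on tests per consultation, any T ≥ k leaves *every* undetermined. T < k rules it out only if k is known and each test counts for one consultation. Section 12.1 does not use k.

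**Step 3. How far apart could the percentages be?** Three inputs are needed and none is in the document: consultations per patient (k), the chance of a test before each (p), and the within-patient correlation (r). All values below are assumptions.

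Independent consultations (r = 0): at least one = 1 − (1 − p)^k; every = p^k.

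Correlated consultations (beta-binomial): a = p(1/r − 1), b = (1 − p)(1/r − 1). Every is the product over i = 0, …, k − 1 of (a + i)/(a + b + i). At least one is 1 minus the same product with b + i in the numerator.

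Worked case, p = 0.7, r = 0.5, k = 4, so a = 0.7 and b = 0.3:
- every = 0.7 × 0.85 × 0.9 × 0.925 = 0.495
- at least one = 1 − 0.3 × 0.65 × 0.7667 × 0.825 = 0.877

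| p | r | k | At least one | Every |
|---|---|---|---|---|
| 0.7 | any | 1 | 70.0% | 70.0% |
| 0.7 | 0.5 | 2 | 80.5% | 59.5% |
| 0.7 | 0.8 | 4 | 77.5% | 62.1% |
| 0.7 | 0.5 | 4 | 87.7% | 49.5% |
| 0.7 | 0 | 4 | 99.2% | 24.0% |
| 0.9 | 0.8 | 4 | 93.1% | 86.5% |

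The r = 0 row is an extreme, since app use is likely to be habitual.

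**Step 4. Staggered entry.** Four consultations for everyone is generous when recruitment runs through the study. Suppose recruitment is even over 12 months, consultations are 3-monthly, only those after recruitment count, p = 0.7 and r = 0.5. At 12 months k is then 0, 1, 2 or 3, each for 25% of recruits.
- Among those with k ≥ 1: at least one = (70.0 + 80.5 + 85.0)/3 = 78.5%; every = (70.0 + 59.5 + 53.6)/3 = 61.0%.
- With all recruits in the denominator and k = 0 counted as not met: 78.5 × 0.75 = 58.9%; 61.0 × 0.75 = 45.8%.

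The gap between definitions remains, and the handling of recruits with no later consultation moves both figures. With 6-monthly consultations under the same rules nobody has more than one by month 12, and the gap disappears.

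**The case against.** The strongest reply is that the synopsis and Section 6 contain no quantifier. Their phrase could loosely mean each consultation, in which case Section 12.1 makes the outcome specific and does not contradict it. That is a possible reading, and it rules out treating *at least one test ever* as the settled intention. It does not rescue the plan: the definition would then be unclear in two places, and the calculation would still start from a total that cannot produce it.

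It can also be said that the data are recoverable. The spreadsheet has date and event columns, and under Section 9.2 (Screening) "Patients will be screened every week according to the scheduled clinic phone calls or visits", so tests could be matched to consultations. If at most one test were logged per consultation, the total compared with the number of consultations would be enough. Both points are fair. They show that a correct derivation is possible, not that Section 12.1 specifies one. Because a consultation without a test has no code, the log may also miss consultations that *every* must count.

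Two stronger inferences are tempting and not supported. A reader might infer that one version must show uptake rising from 3 to 12 months and the other falling. That holds only for cumulative counting in a fixed group. The document does not say that each time point is cumulative, recruitment spans the whole study period, and Section 7 describes the 3-monthly analyses as quality assurance, with final statistics at the end. A reader might also infer that recruits who never confirm download have no place in the denominator. Sections 12.1 and 12.3 refer to each recruited patient and to all participants, which largely settles that they stay in with a count of zero.

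**Conclusion.** The point holds as a fault of wording and derivation. The only primary outcome is stated without a quantifier in two places and with *every* in a third, and the calculation in Section 12.1 cannot give the quantity it names once a patient has two or more consultations. This is wrong as written, not merely short of detail.

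The existence of the fault needs no assumptions beyond some participants having more than one consultation. Its size cannot be fixed from the document. It is zero at one consultation. At four consultations and p = 0.7 it is about 15 percentage points (r = 0.8) to 38 (r = 0.5); at p = 0.9 and r = 0.8 it is under 7. These are illustrations, not predictions. Nothing suggests that a decision would be reversed. The result at risk is the headline percentage, which could be ambiguous or miscomputed, so this should be fixed before the final analysis.

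**What to change.** Put one explicit definition in the synopsis, Section 6 and Section 12.1, and match the derivation to it. The choice belongs to the investigators.

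- If the outcome is *at least one test*: count participants with a total of 1 or more, among all recruited participants, at each stated time point. The planned total already supports this.
- If it is *every consultation*: derive it from dated consultation and APP-6MWT records, not from the total, and log every consultation, including those without a test.

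The other version can be reported as a labelled secondary figure. In either case, state whether the consultation at which a patient is recruited counts, and whether recruits with no later consultation by a time point stay in the denominator.

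The cost is a few reworded sentences, with no extra patients or visits. Only if the *every* figure is kept do clinicians add one yes/no entry per consultation.
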